23. REGULATORY AND HEALTH AUTHORITY AUDITS

The European Union's authorities and/or the Food and Drug Administration (FDA) and/or the local state health authorities may request access to all study records, including source documents for inspection. The investigator and hospital staff are requested to cooperate with these audits. The investigator must notify the sponsor of any health authority audit as soon as notification of such audit is made. A representative or designee of the sponsor may also conduct similar audits and may be present during health authority audit.

24. ELECTRONIC REPORTING OF DATA

All medical data in this trial are to be recorded directly in the EDC (Electronic Data Capture) system. Documentation on paper will be restricted to exceptional circumstances only.

The investigator must ensure the accuracy, completeness and timeliness (and legibility in case of documentation on paper) of data.

Patients will also have access to this EDC to complete their diaries online.

Both sites and patients will get trained on how to access and use the EDC and will be foreseen with a personal user login and password.

25. RECORD RETENTION

It is required that a copy of all records (e.g., informed consent documents, source documents, safety reports, study device dispensing record, etc.) which support case report forms for this study, be retained in the files of the responsible investigator for a minimum of fifteen (15) years following notification by the sponsor that all investigations (not merely the investigator's portion) are completed, terminated and/or discontinued. If the

Doc No: 220CLD

Rev: 03 Date: August 26, 2016

Page 63 of 93

principal investigator retires, relocates, or for other reasons withdraws from the responsibility of keeping the study records, custody must be transferred to a person who will accept the responsibility. Vibrant Ltd. must be notified in writing of the name and address of the new custodian.

26. PROTOCOL MODIFICATIONS

An amendment to the protocol may be proposed by an investigator. The amendment will be prepared and approved by the sponsor according to the sponsor's relevant SOP. The amendment must be submitted to the EC. When applicable, the amendment's implementation will take place only once approved by the EC.

If for any unexpected reasons, there is any requirement to deviate from the treatments stated above, the protocol deviation should be discussed with a Vibrant Ltd. representative.

27. PUBLICATION POLICY

All information concerning this study that was not previously published is considered confidential information. This confidential information shall remain the sole property of Vibrant Ltd.; it shall not be disclosed to others without written consent of Vibrant Ltd. and shall not be used except in the performance of this study.

Any investigator involved with this study is obligated to provide the Sponsor with complete test results and all data derived from the study.

28. SUBJECT / STUDY DISCONTINUATION

Subjects should be removed from the study whenever considered necessary for their welfare or when the subject expresses a desire to withdraw from the study. Noncompliance with the protocol, the occurrence of a Serious Adverse Event or any medical condition that, in the opinion of the investigator, warrants discontinuation from the study for the safety of the subject, may necessitate discontinuing a subject. If a subject is discontinued, the reason must be entered on the case report form and signed by the investigator. In case of any questionable situation, the study monitor or Vibrant Ltd. personnel should be consulted. When a subject is removed from the study as a result of Serious Adverse Event, a final physical examination must be performed. Subjects removed from the study because of an adverse event will be followed-up until the adverse event has been resolved.

In the case that the occurrence of adverse events is greater than anticipated, the clinical investigation will be suspended; in such a case, a safety committee will be arranged to decide if the study could be continued. The Ethics Committee will be notified and the results of the safety committee discussions will be brought for the EC review and decision.

Doc No: 220CLD

Rev: 03 Date: August 26, 2016

Page 64 of 93

Early termination could be a result of:

1. Withdrawal of informed consent by the subject.

- 2. Patients who after inclusion develop medical diseases which may affect the function and interpretation of study results.
- 3. Serious protocol deviation.
- 4. Non-compliance with medical device administration or study procedures as determined by the sponsor.
- 5. Change in subject's condition.
- 6. Patient is Lost to follow-up.
- 7. Confirmed pregnancy.
- 8. Regulatory authorities stop the trial.

During the study, patients exiting the trial will be replaced with new patients, in order to have 120 patients at the end of the trial.

Vibrant Ltd., reserves the right to discontinue any study for administrative reasons at any time, such as, but not limited to a decision to discontinue further clinical investigation with the device, improper conduct of the study by the investigator, inability to obtain the number of subjects required by the protocol, etc. Reimbursements for reasonable expenses will be made if such an action is necessary.

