15.7 Screening visit (day -14)

At the screening visit, subjects will be evaluated for eligibility and undergo physical examination, digital rectal examination, vital sign measurements and blood tests. They will undergo a thorough interview about their constipation and the Rome III questionnaire (see appendix C) will be completed. The Bristol Stool Scale (see Appendix A) will also be completed by the patient.

The investigator will confirm their eligibility and their physical and mental suitability to participate in this study.

Patients exiting the trial at this stage will be considered screening failure patients and be replaced with new patients to reach the goal of 120 patients.

The patient will be trained by the study coordinator to access and use the eDiary. The eDiary contains questions about bowel movements and their associated clinical symptoms (straining, abdominal pain, abdominal discomfort, abdominal gas, bloating, abdominal pain during defecation, need for digital maneuver, sensation of complete evacuation), usage of rescue medication and usage of other medication or supplements (name of drug, dosage, number of takes per day, reason for medication). The information will be transferred to the eCRF every day.

The patient will define his/her preferred device to use the eDiary. The patient and study coordinator will define together the time of the day during which the patient will fill in the eDiary and a daily alert will be set up on the phone of the patient. The daily diary can be found in Appendix D.

Doc No: 220CLD

Rev: 03 Date: August 26, 2016

Page 45 of 93

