17.4 Sample size

The chosen sample size is 120 subjects who will be enrolled and complete the 6 treatment weeks.

The final sample size will be determined following the completion of the interim analysis, based on the efficacy of the new frequency of vibration capsule.

The sample size account for a potential 10% of drop-outs.

The sample size will be increased to at least 134 to account for a potential 10% of dropouts, as needed.

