22. INFORMED CONSENT

Written informed consent must be obtained from each study subject. The subject will be asked to read the informed consent form and to sign the form to indicate consent to participate in the study.

The investigator will explain carefully to the subject the research nature of the study. The scope and aims of the research will be described together with known or foreseeable benefits, risks and discomforts that subjects may experience. Appropriate alternative treatments will be discussed so that the subject may determine whether or not he or she wishes to participate in the study. The subject must understand that throughout the study his or her participation remains voluntary and protected by the Declaration of Helsinki. The investigator is responsible for obtaining written (or witnessed) informed consent from potential subjects prior to study entry. Subjects will be given time to read the informed consent and ask any questions before being asked to sign the form. The informed consent (approved by the sponsor and the Ethics Committee) must be signed and dated by the subject and the investigator. One copy of the signed consent will be

Doc No: 220CLD

Rev: 03 Date: August 26, 2016

Page 62 of 93

given to the subject, a second copy will be sent to the referral investigator and the original will be retained by the investigator.

Subjects may withdraw their consent to participate in the study at any time without prejudice. The investigator may withdraw a subject if, in his clinical judgment, it is in the best interest of the subject or if the subject cannot comply with the protocol. Attempts should be made to complete any examinations and the sponsor must be notified of all withdrawals.

Should a protocol amendment be made, the subject's consent form may be revised to reflect the changes of the protocol. It is the responsibility of the investigator to ensure that an amended informed consent is approved or reviewed by the EC, and that it is signed by all subjects subsequently entered in the study and those currently in the study, if affected by the amendment.

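### Section 28 does not separate stopping capsules from leaving the study and keeps no diary after exit, so treated patients removed early drop out of the primary success rate

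*Combined protocol and SAP*

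**What the plan says.** Section 28 lists eight possible causes of early termination. Item 3 is serious protocol deviation and item 4 is "Non-compliance with medical device administration or study procedures as determined by the sponsor". No level of missed capsules or missed diary days is given. Section 22 lets the investigator withdraw a subject "if the subject cannot comply with the protocol". For withdrawals in general, it asks only that attempts be made to complete examinations. Follow-up after exit is otherwise required in Section 28 only for adverse events, plus a final physical examination after removal for a serious adverse event.

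Section 28 also says that "patients exiting the trial will be replaced with new patients, in order to have 120 patients at the end of the trial". Section 17.4 describes the target in the same terms: "The chosen sample size is 120 subjects who will be enrolled and complete the 6 treatment weeks". It adds: "The sample size will be increased to at least 134 to account for a potential 10% of dropouts, as needed".

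Other provisions that bear on the point:

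- Section 15.9 sets enrolment at the first capsule, so an enrolled patient who exits has been treated.
- Section 17.2.1 makes a patient with fewer than two valid diary weeks (at least five days each) non-evaluable. Success needs three weeks out of six.
- Section 17.8.8 rules out imputation.
- Section 17.7.1 puts every patient who took a capsule in FA, apart from analyses for which there is no valid post-baseline assessment.
- Section 17.7.2 removes major protocol violators from PP without listing the violations.
- Section 17.7.3 makes PP the main efficacy set and repeats the primary assessment on FA.
- Section 17.5 confirms an open-label, single-arm design. On the eDiary, Section 15.7 states: "The information will be transferred to the eCRF every day".

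**The concern.** A patient who is not responding may well start to miss capsules or diary days. If that leads to early termination, the diary ends with participation. The primary endpoint is built entirely from diary weeks, so the timing of removal decides whether the patient counts as a failure or disappears from the denominator.

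The decision is discretionary: there is no threshold, and Sections 22 and 28 name different parties as judging compliance. It is taken in an open-label study in which bowel-movement data arrive daily. With a single arm, no comparison group would share the distortion. What is at stake is whether the reported success rate describes all treated patients or only those who stayed, with the confidence interval reflecting sampling error alone.

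**Working it through.** **The plan's own figure.** Inflating 120 completers for 10% drop-out gives 120 / (1 - 0.10) = 133.3, rounded up to 134. This matches Section 17.4. The synopsis reports no formal sample size calculation, so there is no power or effect size to reproduce.

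**What happens to a treated patient who is removed and gives no further diary data**

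| Point of removal | FA | PP |
|---|---|---|
| Before two valid diary weeks | Non-evaluable, not imputed: absent | Absent |
| After two valid weeks, fewer than three successful | Evaluable, cannot succeed: failure | Failure, or absent if classed as a major violator |
| After three successful weeks | Success | Success, or absent if classed as a major violator |

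**Size in FA.** The documents give no success rate and no data linking removal to outcome, so the following are assumptions: 40% success in patients who stay and 10% in those removed, had they been followed. Let q be the proportion removed and e the share of removals that come before two valid weeks. Every later removal is counted as a failure.

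- All-treated rate: T = (1 - q) × 40% + q × 10%.
- Observed FA rate: F = (1 - q) × 40% / (1 - q × e).
- Bias: F - T.

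For q = 10%, T = 36% + 1% = 37%. For q = 20%, T = 32% + 2% = 34%.

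| q | e = 0 | e = 0.5 | e = 1 |
|---|---|---|---|
| 10% | 36/1.00 = 36.0%, bias -1.0 | 36/0.95 = 37.9%, bias +0.9 | 36/0.90 = 40.0%, bias +3.0 |
| 20% | 32/1.00 = 32.0%, bias -2.0 | 32/0.90 = 35.6%, bias +1.6 | 32/0.80 = 40.0%, bias +6.0 |

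The sign changes where 1 - q × e = (1 - q) × 40% / T. For q = 10%, 36/37 = 0.973, so e = 0.027/0.10 = 0.27. For q = 20%, 32/34 = 0.941, so e = 0.059/0.20 = 0.29. Under these assumptions FA overstates success once more than about 27% to 29% of removals are early.

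**Size in PP.** If every removed patient is also classed as a major violator, PP contains only stayers and reads 40%, whatever the timing. The bias is then +3.0 or +6.0 points. If none is, PP behaves like FA as far as removals are concerned.

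**Outer bound without the 10% assumption.** Take 120 completers and the 14 planned exits (134 - 120), with every exit both excluded and a true failure. A completer rate of 30%, 50% or 70% becomes 36/134 = 26.9%, 60/134 = 44.8% or 84/134 = 62.7%. The most that could be overstated at 10% exits is therefore 3.1, 5.2 or 7.3 points.

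**Scale.** The exact 95% interval for 48/120 (40%) is 31.2% to 49.3%, a half-width of about 9 points.

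**The case against.** A reader might infer that replacement to 120 swaps treated failures for fresh patients and so raises the success rate by 3 to 6 points. The documents do not support that. FA is every patient given a capsule, and neither analysis set is defined as the last 120. Replacement adds patients and deletes none: on the assumptions above, 108 stayers and 120 stayers both have an expected rate of 40%. The bias comes from exclusion, through the evaluability rule and the PP definition. In FA the full 3 to 6 points needs every removal to come before two valid weeks, and with late removals the sign reverses.

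A reader might also infer that the 134 and the replacement rule count drop-out twice. The words as needed in Section 17.4 allow the 134 to be read as the replacement allowance itself.

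Nor do the documents show the sponsor using outcomes to decide who is removed. Sections 22 and 28 are both permissive and can be read as parallel grounds, and the investigator must sign the reason for discontinuation. The stated response to a missed diary entry (Section 15.9) is a phone call the next day, not removal. Withdrawals are explained on the case report form (Section 18) and reported, with Kaplan-Meier time to withdrawal (Section 17.8.4). The study is a mainly descriptive pilot.

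All of that stands. It does not close the gap: reporting withdrawals does not put an early exit back into the success rate, and attempting examinations does not supply diary weeks.

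**Conclusion.** The point holds as a gap in follow-up and in the analysis denominator. A treated patient removed before two valid diary weeks is lost to the primary result in both sets. One removed later without three successful weeks is a failure in FA but may still leave PP, because major violations are not listed.

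Under the assumed 40% and 10% rates, and with later removals counted as failures, the FA bias is -1.0 to +3.0 points at 10% removed and -2.0 to +6.0 at 20%. The upper ends are about one third and two thirds of the half-width of the interval at 48/120. PP can reach those upper ends without any removal being early. That removed patients do worse is plausible but not documented. That the diary stops at exit follows from the absence of any provision to continue it; it is not written outright. The change is a cheap improvement to the plan, not a correction of an error that invalidates it.

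**What to change.** 1. In Section 28, distinguish capsules stopped from study left. State that treated patients who stop capsules or deviate continue the eDiary, the existing calls and visits 3 and 4 to day 42, unless they withdraw consent for follow-up or are lost.
2. In Section 17.7, state that all treated patients, including any later replaced, stay in the FA primary analysis, and report the FA result beside PP.
3. Add a sensitivity analysis on FA that counts treated patients with fewer than two valid diary weeks as non-successes. Under the assumptions above this is the e = 0 column, which lies slightly below the all-treated rate, so it gives a low-side check on the main result.
4. Reconcile Sections 22 and 28 on who judges non-compliance. The grounds for stopping capsules remain with the sponsor and investigator and are not addressed here.

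The cost is protocol wording, a few weeks of additional diary data and already planned contacts for a minority of patients, and one more table. The reported success rate may be lower. Patients who withdraw consent for follow-up or are lost will still be missing, which is why item 3 is needed as well as item 1.

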29. DEVICE ACCOUNTABILITY

Complete traceability records will be kept of all devices during the study. Vibrant devices and relevant accessories will be provided by Vibrant Ltd., bearing required labeling. Device number will be documented in patient medical records, CRF and in center log.

Each clinical investigator will be responsible for the safe storage with restricted access of the investigational materials in their possession, thereby preventing use of any materials by any persons not participating in the study.

After completion of the study, all unused devices must be returned in their original package to Vibrant Ltd. [name]. All investigators will be responsible for using the products according to the IFU and protocol and maintaining product inventory and records.

Doc No: 220CLD

Rev: 03 Date: August 26, 2016

Page 65 of 93

30. APPENDICES

A. Appendix A – Bristol Stool Scale

- B. Appendix B Full list of Adverse Events Phase 3 clinical investigation
- C. Appendix C Rome III questionnaire and instructions for completion
- D. Appendix D Patient daily diary

APPENDIX A – Bristol Stool Scale

The Bristol Stool Scale:

[figure not shown]

Doc No: 220CLD

Rev: 03 Date: August 26, 2016

Page 68 of 93

Appendix B - Full list of Adverse Events – Phase 3 clinical investigation

[figure not shown]

Doc No: 220CLD

Rev: 03 Date: August 26, 2016

Page 69 of 93

Doc No: 220CLD

Rev: 03 Date: August 26, 2016

Page 70 of 93

APPENDIX C – ROME III (Questionnaire and Instructions for Completion)

Doc No: 220CLD

Rev: 03 Date: August 26, 2016

Page 71 of 93

Doc No: 220CLD

Rev: 03 Date: August 26, 2016

Page 72 of 93

Doc No: 220CLD

Rev: 03 Date: August 26, 2016

Page 73 of 93

Doc No: 220CLD

Rev: 03 Date: August 26, 2016

Page 74 of 93

Doc No: 220CLD

Rev: 03 Date: August 26, 2016

Page 75 of 93

Doc No: 220CLD

Rev: 03 Date: August 26, 2016

Page 76 of 93

Doc No: 220CLD

Rev: 03 Date: August 26, 2016

Page 77 of 93

Doc No: 220CLD

Rev: 03 Date: August 26, 2016

Page 78 of 93

Doc No: 220CLD

Rev: 03 Date: August 26, 2016

Page 79 of 93

Doc No: 220CLD

Rev: 03 Date: August 26, 2016

Page 80 of 93

Doc No: 220CLD

Rev: 03 Date: August 26, 2016

Page 81 of 93

Doc No: 220CLD

Rev: 03 Date: August 26, 2016

Page 82 of 93

Doc No: 220CLD

Rev: 03 Date: August 26, 2016

Page 83 of 93

Doc No: 220CLD

Rev: 03 Date: August 26, 2016

Page 84 of 93

Doc No: 220CLD

Rev: 03 Date: August 26, 2016

Page 85 of 93

Doc No: 220CLD

Rev: 03 Date: August 26, 2016

Page 86 of 93

Doc No: 220CLD

Rev: 03 Date: August 26, 2016

Page 87 of 93

Doc No: 220CLD

Rev: 03 Date: August 26, 2016

Page 88 of 93

[figure not shown]

Doc No: 220CLD

Rev: 03 Date: August 26, 2016

Page 89 of 93

APPENDIX D – Patient Diaries

Doc No: 220CLD

Rev: 03 Date: August 26, 2016

Page 90 of 93

[figure not shown]

Doc No: 220CLD

Rev: 03 Date: August 26, 2016

Page 91 of 93

PART 2A

Doc No: 220CLD

Rev: 03 Date: August 26, 2016

Page 92 of 93

Doc No: 220CLD

Rev: 03 Date: August 26, 2016

Page 93 of 93

PART 2B

			I
		·
